9.2.1.2.6. Major Adverse Cardiovascular Events

Deaths (CV and non-CV), nonfatal MIs, supraventricular arrhythmias, and nonfatal strokes that occur during the treatment period or follow-up period will be adjudicated by an independent adjudication committee in compliance with a study-specific adjudication charter. Investigative sites will also be asked to submit any cases of TIA or hospitalization for unstable angina for adjudication as well to ensure that all true stroke and MI events are captured. Hospitalizations for heart failure and coronary interventions (such as coronary artery bypass graft or percutaneous coronary intervention) will also be submitted for adjudication.

Cardiovascular event definitions will be based on the Standardized Definitions for Cardiovascular and Stroke Endpoint Events in Clinical Trials (Hicks et al. 2015) and the ESC/ACCF/AHA/WHF Expert Consensus Document Third Universal Definition of Myocardial Infarction (Thygesen et al. 2012). An adjudication committee will enter the results of adjudication in the corresponding eCRF page.

9.2.1.2.7. Thyroid C-Cell Hyperplasia and C-Cell Neoplasms

Individuals with personal or family history of certain thyroid or nonthyroid endocrine abnormalities or certain preexisting laboratory and genetic characteristics will be excluded from the study (see Section 6.2). The assessment of thyroid safety during the trial will include reporting of thyroid TEAEs and measurements of calcitonin according to Section 2 at screening, baseline, and Visits 11 and 16 (Months 3 and 6) or ET visit. The purpose of calcitonin measurements is to assess the potential of LY3298176 to affect thyroid C-cell function, which includes development of C-cell hyperplasia and neoplasms.

Patients who develop serum calcitonin increases $\geq 50\%$ of the mean of the baseline and screening values AND an absolute value ≥ 20 pg/mL and ≤ 35 pg/mL at Visits 11 and 16 (Months 3 and 6) will be asked to repeat the measurement within 1 month. If this repeat value is increasing ($\geq 10\%$ increase), the patient will be encouraged to undergo additional endocrine assessment and longer term follow-up by an endocrinologist to exclude a serious adverse effect on the gland.

Patients with an increase in serum calcitonin $\geq 50\%$ of the mean of the baseline and screening values AND an absolute value ≥ 35 pg/mL at Visits 9 and 12 (Months 3 and 6) will be recommended to immediately undergo additional endocrine assessments and longer term follow-up by an endocrinologist.

For patients who require additional endocrine assessment because of increased calcitonin concentration per criteria provided in this section, data from the follow-up assessment will be collected in the specific section of the eCRF.

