6.2. Exclusion Criteria

Patients will be excluded from study enrollment if they meet any of the following criteria at screening:

Medical Conditions

- [9] Have type 1 diabetes mellitus.
- [10] Have uncontrolled diabetes defined as more than 2 episodes of ketoacidosis or hyperosmolar state requiring hospitalization in the 6 months prior to Visit 1.

- [11] Have had more than 1 episode of severe hypoglycemia, as defined by the occurrence of neuroglycopenic symptoms requiring the assistance of another person for recovery, within 6 months prior to Visit 1, or has a history of hypoglycemia unawareness or poor recognition of hypoglycemic symptoms. Any patient that the investigator feels will not be able to communicate an understanding of hypoglycemic symptoms and the appropriate treatment of hypoglycemia should also be excluded.
- [12] Have a history of acute or chronic pancreatitis or elevation in serum lipase/amylase (greater than 2 times the upper limit of normal [ULN]) or fasting serum triglyceride level of >500 mg/dL at screening.
- [13] Have a diagnosis of gastroparesis or history of bariatric surgery or a clinically significant gastric emptying abnormality, in the opinion of the investigator.
- [14] Have active proliferative diabetic retinopathy.
- [15] Have known liver disease, obvious clinical signs or symptoms of liver disease, acute or chronic hepatitis, or alanine aminotransferase (ALT) levels >2.5 times the ULN at Visit 1, as determined by the central laboratory at screening.
- [16] Have a known self or family history (first-degree relative) of multiple endocrine neoplasia type 2A or type 2B, thyroid C-cell hyperplasia, or medullary thyroid carcinoma.
- [17] Evidence of hypothyroidism or hyperthyroidism based on clinical evaluation and/or an abnormal thyroid-stimulating hormone that, in the opinion of the investigator, would pose a risk to patient safety. Subjects on a stable dose of thyroid replacement therapy for at least the prior 3 months who are clinically euthyroid and who are anticipated to remain on this dose throughout the trial period may be eligible if they meet the other criteria.
- [18] Have a screening calcitonin ≥20 pg/mL as determined by the central laboratory at Visit 1.

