7.2.2. Specific Restrictions/Requirements

Prior to beginning the study, patients will complete informed consent and baseline tests.

Throughout the study, patients may undergo medical assessments and review of compliance with restrictions before continuing in the study.

Patients will report to the clinical research site for safety assessments and will remain in the clinic until all procedures for that visit are complete and the investigator has deemed it safe to release the patient from the clinic. There will be no inpatient stays. In addition, patients will report to the clinical research site for PK-specific visits (Visits 5, 7, 9, and 12).

Meals/Diet – Patients shall fast for at least 8 hours overnight prior to each outpatient visit where fasting samples are drawn or weight measurements taken.

Alcohol – Alcohol will not be permitted 8 hours prior to the dosing day, until the patient has been discharged from the clinical research site.

Exercise – Patients will be advised to maintain their regular levels of physical activity/exercise during the study. When certain study procedures are in progress at the site, patients may be required to remain recumbent or sitting.

Blood donation – Study participants should be instructed not to donate blood or blood products during the study or for 8 weeks following the study.

Contraception – Male patients or their female partners of child-bearing potential must use reliable contraception during intercourse throughout the treatment period and for 3 months after the last dose of study drug (as the risk of LY3298176 to the unborn fetus is unknown). Female patients of childbearing potential, if sexually active, should use two forms of effective contraception, where at least one form is highly effective for the duration of the trial and for 30 days thereafter. Please see Appendix 7 for further details regarding contraception.

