8.2. Discontinuation from the Study

Some possible reasons that may lead to permanent discontinuation include the following:

- Enrollment in any other clinical trial involving an investigational product or enrollment in any other type of medical research judged not to be scientifically or medically compatible with this study
- Sponsor decision
 - Participation in the study needs to be stopped for medical, safety, regulatory, or other reasons consistent with applicable laws, regulations, and Good Clinical Practice (GCP).

- Investigator decision
 - o The investigator decides that the patient should be discontinued from the study
- Subject decision
 - The patient requests to be withdrawn from the study.

Patients who discontinue the study early will have end-of-study procedures performed as shown in the Schedule of Activities (Section 2).

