9.4.4. Safety Monitoring

Lilly will periodically review evolving aggregate safety data within the study by appropriate methods. In addition, the study team will review safety reports in a blinded fashion according to the schedule provided in the Trial-Level Safety Review plan. Lilly will also review SAEs within time frames mandated by company procedures. The Lilly CRP/CRS will, as appropriate, consult with the functionally independent Global Patient Safety therapeutic area physician or clinical scientist.

In addition, specific safety measures are included in the protocol to ensure appropriate monitoring of pancreatic, thyroid, and liver safety. Laboratory findings that trigger pancreatic and thyroid safety monitoring per Lilly standards are provided in Sections 9.2.1.2.5 and 9.2.1.2.7, respectively. Details of liver safety monitoring are provided in Section 8.1.1. If a study patient experiences elevated ALT $\geq 3 \times$ ULN or elevated total bilirubin $\geq 2 \times$ ULN, clinical and laboratory monitoring should be initiated by the investigator. Details for hepatic monitoring depend upon the severity and persistence of observed laboratory test abnormalities. To ensure patient safety and comply with regulatory guidance, the investigator is to consult with the Lilly CRP/CRS regarding collection of specific recommended clinical information and follow-up laboratory tests (see Appendix 4).

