Appendix 6. Pharmacokinetics Schedule of Events

Study Phase	Screen	Lead- in	Randomize		Treatment Phase													
Visit	1	2	3	4	5	6	7	8	9	10	11	12	13	14	15	16	801	
Month of treatment		0	0	0	0	0	0	1	1	2	3	3	4	5	6	6	(7)	
Week of treatment	-3	-2	0	1	1	2	2	4	4	8	12	12	16	20	24	26	(30)	
Study day/(Dose number)		±7d	0/(1)	7/(2)		14/(3)		28/(5)		56/(9)	84/(13)		112/(17	140/(21)	168/(25)	182/(27)		
PK-specific visit					X		X		X			X						
PK blood draw				X*	X		X		X	X*	X*	X				X*		X

- [I] Predose PK samples will be collected at Visit 4 (Week 1), Visit 10 (Week 8), Visit 11 (Week 12), and Visit 16 (Week 26). $X^* = Predose sample$.
- [II] Postdose PK samples will be collected per the assigned schedule after dosing at Visit 5 (Week 1), Visit 7 (Week 2), Visit 9 (Week 4), and Visit 12 (Week 12), and at early termination from all patients. An early termination PK sample may be taken at any time during the visit.
- 1. At Visit 5 (Week 1), 1 predose PK sample should be collected prior to administering study drug from all patients. Later in the week (Visit 5), an additional PK sample should be taken within 1 to 48 hours (i.e., within 2 days of administrating study drug).
- 2. At Visit 7 (Week 2), 1 PK sample should be collected after administration of the study drug within 1 to 48 hours (i.e., within 2 days of administrating study drug).
- 3. At Visit 9 (Week 4), 1 PK sample should be collected after administration of the study drug within 48 to 72 hours (i.e., 2 to 3 days after the administration of study drug).
- 4. At Visit 12 (Week 12), 1 predose PK sample should be collected prior to administering the study drug from all patients. Later in the week (Visit 12), an additional PK sample should be taken within 96 to 168 hours (i.e., any time between 4 days after study drug administration up to just prior to the next dose of study drug administration).

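### The urgent calcitonin rule (35 pg/mL or more) is tied to two visits with no calcitonin sample, and neither calcitonin rule covers the early-termination sample

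*Protocol*

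**What the plan says.** Protocol Section 9.2.1.2.7 opens by stating when calcitonin is measured: "at screening, baseline, and Visits 11 and 16 (Months 3 and 6) or ET visit". The calcitonin row of the Schedule of Activities (Protocol Section 2, repeated in SAP Appendix 1) agrees.

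The section then gives two action rules. Both require a rise of at least 50% over the mean of the screening and baseline values.

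- **Lower rule**, for values from 20 up to 35 pg/mL: patients who qualify "at Visits 11 and 16 (Months 3 and 6) will be asked to repeat the measurement within 1 month".
- **Upper rule**, for values of 35 pg/mL or more: patients who qualify "at Visits 9 and 12 (Months 3 and 6) will be recommended to immediately undergo additional endocrine assessments".

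Protocol Section 9.4.4 relies on this text as the operative trigger: "Laboratory findings that trigger pancreatic and thyroid safety monitoring per Lilly standards are provided in Sections 9.2.1.2.5 and 9.2.1.2.7, respectively". For patients who leave early, Section 8.2 says: "Patients who discontinue the study early will have end-of-study procedures performed as shown in the Schedule of Activities". Those procedures include a calcitonin sample.

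**The concern.** The upper rule carries the same month label as the lower rule but different visit numbers, and those numbers belong to PK-only visits. Read literally, the more serious elevation is tied to visits that yield no calcitonin result. A value above 35 pg/mL at Visit 11 or 16 is then too high for the lower rule and at the wrong visit for the upper one. The smaller elevation has a stated action and the larger one has none.

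The early-termination sample is a separate gap. It is drawn, but neither rule says what to do with the result, and the month label does not help there.

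At stake is consistent follow-up of a thyroid safety signal across sites. Section 9.2.1.2.7 also uses these criteria to decide whose endocrine follow-up data go into a dedicated part of the eCRF, so the wording affects data capture as well as care.

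**Working it through.** No sample size, power or error rate is involved, and there is no plan figure to reproduce. The check sets the schedule against the rules.

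**Step 1. Which visits have a calcitonin sample?** Reading the Schedule of Activities by column, with months from Protocol Appendix 6:

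| Visit | Week | Month | PK-specific | Calcitonin |
|---|---|---|---|---|
| 1 (screening) | -3 | – | no | yes |
| 3 (baseline) | 0 | 0 | no | yes |
| 9 | 4 | 1 | yes | no |
| 11 | 12 | 3 | no | yes |
| 12 | 12 | 3 | yes | no |
| 16 | 26 | 6 | no | yes |
| Early termination | – | – | no | yes |

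Protocol Section 7.2.2 confirms that Visits 9 and 12 are PK-specific. Appendix 6 confirms their timing in its list of postdose PK samples: "Visit 9 (Week 4), and Visit 12 (Week 12), and at early termination from all patients". These two visits fall in Months 1 and 3, so the upper rule's visit numbers also contradict its own label of Months 3 and 6. Visits 11 and 16 match that label.

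**Step 2. How many scheduled post-baseline samples does each rule name?** The set is {11, 16, early termination}, 3 sampling points.

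- Upper rule {9, 12}: 0 of 3.
- Lower rule {11, 16}: 2 of 3.
- Both rules after correction {11, 16, early termination}: 3 of 3.

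No patient is expected to give all three, because early termination replaces completion. By type of patient:

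| Patient | Scheduled post-baseline samples | Upper rule names | Lower rule names |
|---|---|---|---|
| Completer | 11, 16 | 0 of 2 | 2 of 2 |
| Leaves after Visit 11 | 11, early termination | 0 of 2 | 1 of 2 |
| Leaves before Visit 11 | early termination | 0 of 1 | 0 of 1 |

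**Step 3. Could the 50% condition be what decides?** The condition is value ≥ 1.5 × mean(screening, baseline). Exclusion criterion 18 removes patients who "Have a screening calcitonin ≥20 pg/mL as determined by the central laboratory at Visit 1". The Visit 3 value is not restricted, so assume that it is also below 20 pg/mL. Then 1.5 × 20 = 30, which is below 35, and every value of 35 or more already meets the condition. This holds up to a mean of 35 / 1.5 = 23.3 pg/mL. Under that assumption, the visit wording is the only part of the upper rule that a value of 35 or more can fail.

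**Step 4. How many patients could depend on the early-termination sample?** The protocol plans for 10% dropout among about 300 randomized: 0.10 × 300 = 30. At the planned rate, up to about 30 patients could have early termination as their last scheduled calcitonin sample. This is a ceiling at that rate, since some would give no sample. It counts patients sampled, not patients with raised values.

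**Step 5. Was it corrected?** The summary for amendment (a) lists changes to Sections 2, 6.3, 7.6, 8.1.1 and 8.1.2 and to Appendix 6. It corrects a day and dose number for Visit 13 but does not touch Section 9.2.1.2.7.

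**The case against.** The best case against is that this is an editorial slip no one could act on. Neither named visit produces a calcitonin result. The month label, the section's opening paragraph, the lower rule and the Schedule all point to Visits 11 and 16. The action is only a recommendation, and no stopping rule or endpoint depends on it.

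There are also general safeguards that apply at any visit. Investigators must document review of each laboratory safety report (Section 9.2). Findings that lead to a diagnosis are reported as adverse events (Section 9.4.3). Study drug can be stopped for a clinically significant laboratory value (Sections 8.1.1 and 8.1.2). SAP Section 6.10.4.6 lists every qualifying value after the first dose without regard to visit. The early-termination point is arguably an omission rather than an error, since that visit can be read as standing in for the remaining scheduled one.

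Most of this stands, and it limits the severity. It does not remove the point. The general safeguards do not specify endocrine referral, and the SAP listing is a reporting output that prompts nothing at the site. The early-termination gap has to be filled by inference. The neighbouring pancreatic enzyme rule in Section 9.2.1.2.5 shows a safer form: it applies throughout the study and deals explicitly with the follow-up visit.

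**Conclusion.** The concern holds. As written, the upper calcitonin rule names none of the 3 scheduled post-baseline sampling points, and the lower rule omits early termination. Followed literally, the more urgent rule never fires on a scheduled sample.

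The intended visits can be inferred, so the consequence is a risk of uneven application between sites. It should be corrected, but it does not threaten the trial's conclusions: the primary analysis and power are untouched.

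The visit mismatch rests only on the documents' own tables. Two supporting statements rest on assumptions: a baseline calcitonin below 20 pg/mL (Step 3) and the planned 10% dropout (Step 4). The documents give no rate of values at or above 35 pg/mL, so the number of patients affected cannot be estimated.

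**What to change.** In Protocol Section 9.2.1.2.7, name Visits 11 and 16 and the early-termination visit in both rules.

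The extracted text has the lower rule running up to and including 35 pg/mL. If the printed protocol reads the same, change it to at least 20 and below 35 pg/mL. A value of exactly 35 then falls only under the upper rule, and not under two different actions.

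For patients already sampled, the SAP Section 6.10.4.6 listing can be used to check that anyone with a qualifying value was followed up.

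The cost is one protocol text correction, with no new samples or visits.

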9.2.2. Complaint Handling

Lilly collects product complaints on investigational products and drug delivery systems used in clinical studies in order to ensure the safety of study participants, monitor quality, and to facilitate process and product improvements.

Patients will be instructed to contact the investigator as soon as possible if he/she has a complaint or problem with the investigational product or drug delivery system so that the situation can be assessed.

9.3. Treatment of Overdose

For patients with suspected or confirmed overdose with LY3298176 or dulaglutide, there is no specific antidote. The patient should be watched for GI symptoms and hypoglycemia. Treatment is supportive, depending on the patient's symptoms.

Refer to the IB for LY3298176 and to the Product Label for dulaglutide.

9.4. Safety

9.4.1. Electrocardiograms

For each patient, 12-lead ECGs should be collected according to Section 2. Patients must be supine for approximately 5 to 10 minutes before ECG collection and remain supine, but awake, during ECG collection.

Electrocardiograms should be recorded in triplicate according to study-specific recommendations included in the Manual of Operations for the study, using standardized equipment provided by the sponsor.

Consecutive replicate ECGs will be obtained at approximately 1-minute intervals. Electrocardiograms may be obtained at additional times, when deemed clinically necessary. Collection of more ECGs than expected at a particular time point is allowed when needed to ensure high-quality records.

Electrocardiograms will initially be interpreted by a qualified physician (the investigator or qualified designee) at the site as soon after the time of ECG collection as possible, and ideally while the patient is still present, to determine whether the subject meets entry criteria and for immediate subject management, should any clinically relevant findings be identified. Any clinically significant findings from ECGs that result in a diagnosis and that occur after the patient receives the first dose of the investigational treatment should be reported to Lilly or its designee as an AE. The investigator (or qualified designee) is responsible for determining if any change in patient management is needed, and must document his/her review of the ECG printed at the time of evaluation.

After enrollment, if a clinically significant increase in the QT/QTc interval from baseline or other clinically significant quantitative or qualitative change from baseline is identified, the patient will be assessed by the investigator for symptoms (e.g., palpitations, near syncope, and syncope) and to determine whether the patient can continue in the study. The investigator or qualified designee is responsible for determining if any change in patient management is needed and must document his/her review of the ECG printed at the time of evaluation from at least 1 of the replicate ECGs from each time point.

All digital ECGs will be obtained using centrally provided ECG machines and will be electronically transmitted to a designated central ECG laboratory. The central ECG laboratory will perform a basic quality control check (e.g., demographics and study details) and then store the ECGs in a database. At a future time, the stored ECG data may be overread by a cardiologist at the central ECG laboratory for further evaluation of machine-read measurements or to meet regulatory requirements.

The machine-read ECG intervals and heart rate may be used for data analysis and report-writing purposes, unless a cardiologist overreading of the ECGs is conducted prior to completion of the final study report (in which case, the overread data would be used).

In addition, for each patient, a single ECG will be recorded at screening and if the patient discontinues from the study prematurely (Section 2) for immediate patient management. These ECGs will be stored at the investigation site.

Any treatment-emergent clinically significant ECG finding resulting in a diagnosis should be reported as an AE in the eCRF.

9.4.2. Vital Signs

Sitting BP and PR will be measured using standardized equipment provided by the sponsor according to Section 2. Vital sign measurements should be taken before obtaining an ECG tracing and before collection of blood samples for laboratory testing, at visits where required (see Section 2). The participant should be required to sit quietly for 5 minutes before vital sign measurements are taken. An appropriately sized cuff (cuff bladder encircling at least 80% of the arm) should be used to ensure the accuracy of BP measurements. The arm used for the BP measurement should be supported at heart level. At Visit 1 (screening), to determine which arm should be used to collect BP and PR throughout the study, BP and PR will be measured once in each arm, and the arm that had the higher systolic BP should be used to collect all 3 measurements of both BP and PR at all study visits. For each parameter (PR, systolic BP, and diastolic BP), 3 measurements will be taken using the same arm; the recordings should be taken at least 1 minute apart, and each measurement of sitting PR and BP will be recorded in the eCRF. Any AE related to changes in BP and PR should be reported.

